6.2.3 Medication History and Concomitant Medications

Analysis Set: Safety Analysis Set

Analysis Variables:

HMG-CoA Reductase Inhibitor
Medication history

Concomitant medications

Analysis Methods: For the above analysis items, the following analysis will be performed for each treatment group. Analysis variables will be coded using the WHO (World Health Organization) Drug. Coded medications will be sorted in frequency order. Medications used more than once within a subject will be counted only once for the subject.

- (1) Summary of frequency distribution of HMG-CoA Reductase Inhibitor
- (2) Summary of frequency distribution of medication history
- (3) Summary of frequency distribution of concomitant medications that started and stopped prior to baseline
- (4) Concomitant medications that were ongoing at baseline and those that started after baseline

6.3 Compliance

6.3.1 Study Medication Compliance

Analysis Set: Safety Analysis Set

Analysis Variables: Study medication compliance (%)

[(Min<= - <50.0, 50.0<= - <=Max]

Time Point: Week 4, Week 8

Analysis Methods: For the above analysis items, the following analysis will be performed for treated with Omega FAE group by time point.

- (1) Summary of frequency distribution

6.3.2 Diet Compliance before Visit

Analysis Set: Safety Analysis Set

Analysis Variables: Any Alcohol from 9:00 PM on 2 days before or 9:00 PM on previous day to Fasting Test? [Yes, No]
Overeat or Overdrink or Extreme Diet Change on the day before fasting test? [Yes, No]

Time Point: Week 4, Week 8

Analysis Methods: For the above analysis items, the following analysis will be performed for each treatment group and all subjects in the analysis set by time point.

- (1) Summary of frequency distribution

6.3.3 Study Medication Exposure

Analysis Set: Safety Analysis Set

Analysis Variables: Duration of exposure (days),

[1<= - <29, 29<= - <57, 57<= - <=Max]

Analysis Methods: For the above analysis items, the following analysis will be performed for each treatment group and all subjects in the analysis set.

- (1) Summary of frequency distribution for categorical variables and summary statistics for continuous variables

7 EFFICACY EVALUATIONS

7.1 Primary Endpoint and the Analytical Methods

Analysis Set: Full Analysis Set

Analysis Variables: Change of sd LDL-C by Lipoprotein fraction and particle size of LDL

Time Point : Week 0, Week 4, Week 8

Stratified Variable: Fasting Triglycerides (Week -4)

[Min<= - <300, 300<= - <Max]

Age (Week -4) [Min<= - <65, 65<= - <Max]

Analysis Methods:

- (1) Summary statistics of observed value and 95% confidence interval for the mean will be calculated by treatment groups and time point. In addition, Mean (+/-SD) plots will be made by treatment group and time point. Mean differences and the 95% confidence interval (two-sided) will also be provided.
- (2) The same analyses described in (1) will be performed on percent change from baseline.
- (3) Subgroup analysis of observed value and percent change from baseline will be conducted by stratified variables described above. Summary statistics, 95% confidence interval for the mean, mean differences and the 95% confidence interval (two-sided) will be provided.
- (4) The same analyses described in (3) will be performed on percent change from baseline.

- (5) ANCOVA (analysis of covariance), with Fasting Triglycerides at week -4 (Min ≤ - <300, 300 ≤ - <Max), and Age at week -4 (Min ≤ - <65, 65 ≤ - <Max) as covariate, Treatment group as independent variable, will be applied to the data of percent change at Week 0 to Week 8. (alpha=0.05 through an ANCOVA strategy)

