6.2 Rationale for the clinical study design

<Rationale>

This clinical study was designed as an open-label study with the control group of patients who will not be treated with omega-3-acid ethyl esters, because the objective is to explore the effects of 8-week, twice-daily, oral treatment with omega-3-acid ethyl esters 2 g on the lipid and lipoprotein profile in the blood in hyperlipidemic patients receiving a HMG-CoA reductase inhibitor. Subjects are to be stratified for allocation (1:1 ratio) by the factors of “fasting TG (< 300 mg/dL or \geq 300 mg/dL) and age (< 65 years or \geq 65 years) at the start of the screening period” that may potentially bias the lipid and lipoprotein profile in the blood, so that the potential bias between the treatment groups is minimized.

<Rationale for the dose regimen>

In accordance with the approved dosage and administration of omega-3-acid ethyl esters, omega-3-acid ethyl esters 2 g is to be orally administered immediately after meal twice daily as the dose regimen in this study. In the Phase 3 confirmatory study in patients with hypertriglyceridemia, superiority of the product 4 g group to the EPA-E group as well as non-inferiority of the product 2 g group to the EPA-E group were confirmed for percentage of change in TG from baseline at the completion of administration of omega-3-acid ethyl esters 2 or 4 g or the control EPA preparation 1.8 g/day. Patients receiving omega-3-acid ethyl esters in actual clinical practice are likely to have increased TG, therefore the dose of 4 g daily was selected as having more marked TG-lowering effect, so that the effects of omega-3-acid ethyl esters on the lipid profiles may be investigated in detail.

<Rationale for the study period>

In the Phase 3 confirmatory study in patients with hypertriglyceridemia, decrease of TG was observed in an early stage (Week 4) after the start of administration with omega-3-acid ethyl

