6.2 Demographics and Other Baseline Characteristics

6.2.1 Distribution of Demographics Items

Analysis Set; Safety Analysis Set, Full Analysis Set

Analysis Variables:

Age(Week -4)(years) [Min<= - <65, 65<=Max]

Age (Week 0) (years) [Min<= - <65, 65<=Max]

Gender [Male, Female]

Height (Week -4) (cm) [Min<= - <150, 150<= - <160,
160<= - <170, 170<= - <=Max]

Weight (Week -4) (kg)
[Min<= - <50.0, 50.0<= - <60.0,
60.0<= - <70.0, 70.0<= - <80.0,
80.0<= - <=Max]

BMI(Week -4)(kg/m²)[Min<= - <18.5, 18.5<= - <25.0
25.0<= - <=Max]

Duration of Hyperlipidemia (years) [Min<5, 5<=Max]

Frequency of Fish Intake [Almost Every Day, About Every Two Days,
About Once or Twice Per Week, Rarely]

Smoking Classification [Never Smoked, Current Smoker, Ex-Smoker]

Drink Alcohol Almost Every Day? [Yes, No]

Fasting Triglycerides(Week -4)(mg/dL)
[Min<= - <300, 300<= - <=Max]

Fasting Triglycerides (Week 0)(mg/dL)
[Min<= - <300, 300<= - <=Max]

Cholesterol Concentration in sd LDL Fraction (Week 0)

Triglycerides Concentration in sd LDL Fraction (Week 0)

Free Cholesterol Concentration in sd LDL Fraction (Week 0)

Phospholipid Concentration in sd LDL Fraction (Week 0)
Particle Size (nm) of LDL (Cholesterol Monitor) (Week 0)
Particle Size (nm) of LDL (Triglycerides Monitor) (Week 0)
Particle Size (nm) of LDL (Free Cholesterol Monitor) (Week 0)
Particle Size (nm) of LDL (Phospholipid Monitor) (Week 0)

Analysis Methods: For the above analysis items, the following analysis will be performed for each treatment group and all subjects in the analysis set.

- (1) Summary of frequency distribution for discrete variables and summary statistics for continuous variables.

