7.3 Other Analyses

Analysis Set: Full Analysis Set

Analysis Variables: Lipoprotein Lipase, HS-CRP

Time Point: Week 0, Week 4, Week 8

Analysis Methods: The same analyses described in 7.1(1), (2) will be performed on the Items described above.

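### For Week 8 percent change, the between-arm difference and CI are unadjusted, the only test is a stratum-adjusted ANCOVA, and no adjusted difference or CI is requested

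*SAP*

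**What the plan says.** Protocol 6.2 gives the allocation scheme: "Subjects are to be stratified for allocation (1:1 ratio) by the factors of" fasting TG (below 300 or at least 300 mg/dL) and age (below 65 or at least 65 years) at the start of screening. The reason given is that these may bias the lipid and lipoprotein profile.

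SAP 7.1 then sets out the following:

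- Item (1), for observed values by arm and time point: "Mean differences and the 95% confidence interval (two-sided) will also be provided". No model or covariate is named.
- Item (2): "The same analyses described in (1) will be performed on percent change from baseline".
- Items (3)-(4): "Subgroup analysis of observed value and percent change from baseline will be conducted by stratified variables described above", again with mean differences and CIs.
- Item (5): an ANCOVA with the Week -4 TG and age categories "as covariate, Treatment group as independent variable, will be applied to the data of percent change at Week 0 to Week 8", at alpha 0.05. The item does not ask for an adjusted treatment difference or a CI.

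SAP 7.2 applies all of 7.1 to the secondary endpoints. SAP 10.1 restates the ANCOVA covariates and refers back to 7.1(5) and 7.2 without adding an output. SAP 7.3 (lipoprotein lipase and hs-CRP) takes only the descriptive part: "The same analyses described in 7.1(1), (2) will be performed on the Items described above". SAP 4 sets a two-sided 5% level, 95% intervals and a display rule for p-values.

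**The concern.** For one quantity, percent change from Week 0 to Week 8, the tables would show an effect and CI from a two-sample comparison beside a p-value from a model with two further terms. Nothing says which is the between-arm result. A CI that includes zero could stand next to an ANCOVA p-value below 0.05, or the reverse, and a reader could pick either.

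Stratified allocation also matters here. It balances the strata between arms, so the raw difference varies less than its usual standard error implies whenever the strata are prognostic. The unadjusted interval is then conservative, and precision that the design has already secured is not reported.

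The pattern is repeated many times. SAP Appendix 1 lists 9 primary variables (5 + 4) and 63 secondary entries (16 + 28 + 1 + 4 + 10 + 4), and SAP 10.5 makes no multiplicity adjustment.

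**Working it through.** **Inputs from the documents.** 50 evaluable patients, 25 per arm (Protocol 13.3, a feasibility figure, so there is no sample size calculation to reproduce). Two binary strata and 1:1 allocation (Protocol 6.1). Two-sided 5% level and 95% CI (SAP 4).

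**Assumed, because the documents give no figure.** The share of outcome variance explained by the strata, R², is 0, 0.05 or 0.10. The true difference is 0, 0.6 or 0.8 SD. Blocks of 4 are used within strata, 20% of patients have TG of at least 300 mg/dL, 40% are aged at least 65, R² is split equally between the factors, and all 50 are analysed.

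**Step 1: width at 25 per arm, in SD units.**

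- Unadjusted half-width: t(0.975, 48) × √(2/25) = 0.5687.
- Adjusted half-width at R² = 0: t(0.975, 46) × √(2/25) = 0.5693.
- In general, adjusted width / unadjusted width = √(1 − R²) × t(46)/t(48), where t(46)/t(48) = 0.5693/0.5687 = 1.001.

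At R² = 0.05 this is √0.95 × 1.001 = 0.976, so the unadjusted interval is 1/0.976 = 1.025 times as wide. At R² = 0.10 it is √0.90 × 1.001 = 0.950, and 1/0.950 = 1.053.

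**Step 2: coverage and disagreement.** 8,000 trials were simulated per setting, comparing the pooled-variance interval with the ANCOVA containing treatment and both strata. Disagreement means that one excludes zero and the other does not.

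| R² (assumed) | Adjusted / unadjusted width | Coverage of unadjusted 95% CI | Disagreement, no effect | Disagreement, 0.6 SD | Disagreement, 0.8 SD |
|---|---|---|---|---|---|
| 0 | 1.001 | 94.5–95.2% | 0.6% | 2.2% | 1.6% |
| 0.05 | 0.976 | 95.4–95.8% | 1.3% | 4.1% | 2.6% |
| 0.10 | 0.950 | 95.9–96.1% | 1.3% | 5.6% | 3.9% |

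At 0.6 SD the totals are made up as follows, with ANCOVA significant and CI including zero given first and the reverse second:

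- R² = 0: 0.92% + 1.30% = 2.2%
- R² = 0.05: 2.80% + 1.26% = 4.1%
- R² = 0.10: 4.76% + 0.88% = 5.6%

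The simulation standard error of a 95% coverage figure is √(0.95 × 0.05/8000), about 0.24 percentage points, so the R² = 0 row is consistent with 95%.

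**Step 3: a second set of assumptions.** With 6,000 trials per setting, 45% aged at least 65 and the explained variance placed on the TG stratum, the unadjusted SE was 1.024 and 1.052 times the adjusted one at R² of 0.05 and 0.10. Disagreement at 80% power was 2.8% and 4.0%, close to the 0.8 SD column.

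**Step 4: scale over the tables.** Over 72 listed entries, 72 × 0.6% = 0.4 and 72 × 5.6% = 4.0, so between none and about four conflicting rows would be expected if one rate applied to all. This is an order of magnitude only.

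**The case against.** The strongest reply is that raw differences shown as description beside a covariate-adjusted model are ordinary practice. The study is exploratory, its size rests on feasibility, and Protocol 13.1.3 plans only per-arm summaries. The unadjusted interval, where it departs from 95% coverage, does so on the safe side. All of this stands, and it limits the point to incomplete output specification. It does not say which result is the main one, and the adjusted estimate is still not requested. That 7.1(1) is unadjusted is the natural reading of a mean difference with no model named, although the SAP does not say so expressly.

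A reader might infer more than the documents support:

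- **That every between-arm estimate ignores the strata.** Items (3)-(4) are computed within levels of those factors. At most, a TG subgroup leaves out age, and an age subgroup leaves out TG.
- **That the CIs are too wide.** This holds only if the strata predict percent change, and no document gives that association. R² of 0.20 or 0.30 would give disagreement of 9.90% + 0.40% = 10.3% or 14.17% + 0.29% = 14.5% at 0.6 SD, but nothing in the documents supports so strong a relation for percent change.
- **That the conflict runs through all the tables.** Observed values, Week 4, the subgroups and the variables in 7.3 have no specified test, so their CIs have no p-value to contradict.
- **That all disagreement comes from leaving out the strata.** Two different statistics disagree in 0.6% to 2.2% of comparisons even at R² = 0.
- **That patients would drop out of the model because 7.1 and 7.2 close the upper category with `<Max`.** SAP 6.2.1 writes "Min<= - <300, 300<= - <=Max" for TG, and 10.1 closes the same ANCOVA covariates with `<=Max`. This is a slip of notation with one sensible reading.

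**Conclusion.** The point holds for percent change from Week 0 to Week 8 in the primary and secondary endpoints. The estimate and CI come from an unadjusted comparison, the only test comes from a stratum-adjusted model, and no adjusted difference or CI is requested. The loss is small: about 2% to 5% in CI width at an assumed R² of 0.05 to 0.10, and none at R² = 0. Disagreement with the p-value affects a few percent of comparisons, and part of that would occur even if the strata had no prognostic value.

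These sizes rest on assumed R², effect sizes, stratum proportions and block size, with 50 patients analysed. The textual mismatch does not depend on them. No error rate is inflated. The harm is inconsistent reporting, and it is avoidable at almost no cost.

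**What to change.** In SAP 7.1(5) and 7.2, state that the ANCOVA-adjusted treatment difference and its two-sided 95% CI are reported with the p-value from the same model, as the main between-arm result for Week 8 percent change. The interval and the test then agree by construction.

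Label the differences in 7.1(1)-(4), and where 7.2 repeats them, as unadjusted and descriptive. They need not be replaced by model estimates. Week 0 observed values only describe baseline, and some subgroups may be very small: at an assumed 20%, TG of at least 300 mg/dL would hold 0.20 × 50 = 10 patients.

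As an editorial correction, change `<Max` in 7.1 and 7.2 to `<=Max`, to match 6.2.1 and 10.1.

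The cost is a few lines of SAP wording and one more output from a model that is already specified. No new data or procedures are needed.

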5.0 STUDY OBJECTIVES AND ENDPOINTS

5.1 Objectives

To explore the effects of 8-week treatment with omega-3-acid ethyl esters on the lipid and lipoprotein profile in the blood in hyperlipidemic patients receiving a HMG-CoA reductase inhibitor by use of HPLC in comparison with the control group of patients not treated with omega-3-acid ethyl esters.

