13.1.3.1 Analysis of the primary endpoint

Change in mean particle sizes of sdLDL-C and LDL-C in the specific 20-lipoprotein fraction assay

[Analytical method]

- 1) At each evaluation time point during the treatment period, summary statistics (number of subjects, mean, standard deviation [SD], minimum value, maximum value, quartiles) and a two-sided 95% confidence interval for the mean will be calculated in each treatment group, and a diagram illustrating the change in the mean \pm SD will be prepared.
- 2) At each evaluation time point during the treatment period, percentage of change (Visit 3 or 4 - Visit 2 in the treatment period) will be calculated in each treatment group and analyzed in the same manner as in the above 1).
- 3) At each evaluation time point during the treatment period, study subjects will be stratified by fasting TG and ages at the start of study drug administration, and summary statistics (number

of subjects, mean, SD, minimum value, maximum value, quartiles) and a two-sided 95% confidence interval for the mean will be calculated and analyzed in each treatment group.

- 4) At each evaluation time point during the treatment period, percentage of change from baseline will be calculated and analyzed in the same manner as in the above 3).

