7.2 Secondary Endpoints and the Analytical Methods

Analysis Set: Full Analysis Set

Analysis Variables:

- (1) Change of lipid component by Lipoprotein Fraction in Major Lipid
- (2) Change of fatty acid in all lipid and sd LDL-C
- (3) Change of serum lipid, lipid concentration of apolipoprotein and lipoprotein and particle number of lipoprotein

* See appendix 1 for detail of items.

Time Point: Week 0, Week 4, Week 8

Stratified Variable: Fasting Triglycerides (Week -4)

[Min ≤ - <300, 300 ≤ - <Max]

Age (Week -4) [Min ≤ - <65, 65 ≤ - <Max]

Analysis Methods: The same analyses described in 7.1 will be performed on the Items described above.

For the Analysis variable 2), exploratory analysis will be performed about relationship between percent change from baseline of sd LDL at Week 8 and percent change from baseline of fatty acid in all lipid at Week 8.

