10.1 Adjustments for Covariates

ANCOVA will be performed on primary and secondary endpoints with Fasting triglycerides at week -4($\text{Min} \leq - < 300$, $300 \leq - \leq \text{Max}$), and Age at week -4($\text{Min} \leq - < 65$, $65 \leq \text{Max}$) as covariate. Details are described in 7.1(5) and 7.2.

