1.1 Primary Endpoint

1) Change of sd LDL-C by Lipoprotein fraction and particle size of LDL

(1) sd LDL-C by Lipoprotein Fraction

Cholesterol Concentration in sd LDL Fraction

Triglycerides Concentration in sd LDL Fraction

Free Cholesterol Concentration in sd LDL Fraction

Phospholipid Concentration in sd LDL Fraction

TG/Cholesterol ratio in sd LDL Fraction

(2) Particle Size of LDL

Particle Size of LDL (Cholesterol Monitor)

Particle Size of LDL (Triglycerides Monitor)

Particle Size of LDL (Free Cholesterol Monitor)

Particle Size of LDL (Phospholipid Monitor)

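### The ANCOVA leaves out the Week 0 value of the variable it analyses and so gives up precision; concentration-type variables also lack a log-scale summary of change

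*SAP*

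**What the plan says.** SAP 7.1(1) summarises observed values by arm and visit, with 95% confidence intervals and between-arm mean differences. For item (2) it states: "The same analyses described in (1) will be performed on percent change from baseline". Item (5) specifies an ANCOVA that "will be applied to the data of percent change at Week 0 to Week 8". Its covariates are Week -4 fasting triglycerides, split at 300 mg/dL, and Week -4 age, split at 65 years. SAP 10.1 confirms that "ANCOVA will be performed on primary and secondary endpoints" and names the same two factors.

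SAP 7.2 carries the methods over to the secondary endpoints: "The same analyses described in 7.1 will be performed on the Items described above". SAP 7.3 does so for lipoprotein lipase and hs-CRP, but without the ANCOVA: "The same analyses described in 7.1(1), (2) will be performed on the Items described above".

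The nine primary variables in SAP Appendix 1, 1.1 are four concentrations in the sdLDL fraction, one ratio ("TG/Cholesterol ratio in sd LDL Fraction") and four measures of LDL particle size.

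Protocol 13.1.3.1 item 2) is the source of the percent-change tables: "percentage of change (Visit 3 or 4 - Visit 2 in the treatment period) will be calculated in each treatment group". Protocol 5.1 sets the aim as exploring effects "in comparison with the control group of patients not treated with omega-3-acid ethyl esters".

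The efficacy sections contain no log transformation, geometric mean, rank method or Week 0 covariate. SAP 8.2.2 adds absolute change, without confidence intervals, for total cholesterol, TG, HDL-C and non-HDL as safety data.

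**The concern.** There are two separate issues.

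**Precision.** Percent change is built from the Week 0 value, so measurement noise at Week 0 feeds directly into it: a patient who happens to read high at Week 0 tends to show a fall. Adjusting for the Week 0 value removes part of that noise and corrects for chance imbalance between arms. The two planned factors are coarse splits of triglycerides and age from an earlier visit and do not do this job for sdLDL cholesterol or LDL particle size. With 25 per arm, chosen on feasibility (Protocol 13.3), precision is scarce.

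**Display of change.** Percent change in a noisy positive variable is right-skewed: halving counts as -50% and doubling as +100%. For concentrations, particle numbers and ratios, the arithmetic mean can therefore sit above zero in an arm whose geometric mean has not moved. The protocol's efficacy methods are per-arm summaries, so a reader may see a rise in an unchanged control arm, or too small a fall on treatment.

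**Working it through.** **Inputs from the documents.** 25 evaluable patients per arm (Protocol 13.3); two-sided 5% level and 95% intervals (SAP 4); ANCOVA response and covariates (SAP 7.1(5), 10.1). The Week 0 value is measured at Visit 2 (Protocol Appendix A), and Protocol 9.3.2 has the Visit 2 tests completed before the patient is notified for allocation. It is therefore a legitimate baseline covariate.

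**Nothing to reproduce.** The documents give no SD, effect size or power, and the sample size is stated not to rest on statistics.

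**Assumptions.** Per-visit within-subject log-SD *s* = 0.1 to 0.5; between-subject log-SD *b* = 0.3, 0.5 or 0.8; true change of none or a 25% fall; log-normal data.

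**Step 1: value of the Week 0 covariate.** Let d = ln(Week 8 / Week 0), with variance 2s². The correlation between visits is ρ = b²/(b² + s²). Regressing d on ln(Week 0) leaves residual variance s²(1 + ρ), so the standard error is multiplied by √((1 + ρ)/2).

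With s = 0.3, the between-arm standard error of mean d without the covariate is √(4 × 0.09/25) = 0.120. A 25% fall is |ln 0.75| = 0.288, which is 2.40 standard errors.

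| b | ρ | SE multiplier | SE with Week 0 | Effect / SE |
|---|---|---|---|---|
| 0.3 | 0.50 | 0.866 | 0.104 | 2.77 |
| 0.5 | 0.74 | 0.931 | 0.112 | 2.57 |
| 0.8 | 0.88 | 0.969 | 0.116 | 2.48 |

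Simulated ANCOVA power (20,000 trials per setting; the two stratification factors always included and assumed unrelated to outcome):

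| Model, s = 0.3 | b = 0.3 | b = 0.5 | b = 0.8 |
|---|---|---|---|
| Percent change, as planned | 62% | 61% | 62% |
| Percent change + Week 0 | 70% | 65% | 62% |
| Log ratio | 65% | 65% | 65% |
| Log ratio + log Week 0 | 76% | 70% | 67% |

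On the log scale the covariate adds 11, 5 and 2 points. On the percent-change scale it adds 8, 4 and 0. The log scale alone adds about 3. Type I error of the log model with log Week 0 is 4.8 to 5.1%.

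The multiplier depends on ρ, not on *s* itself, so the gain is not tied to skewness. For LDL particle size at an assumed s = 0.01 and b = 0.01 or 0.02, ρ = 0.5 or 0.8, and the standard error falls by 13% or 5% before the small loss for one degree of freedom.

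**Step 2: lean of the per-arm percent change.** With no geometric change, the expected mean percent change is 100 × (exp(s²) - 1). Intervals were simulated for 100,000 arms of 25.

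| s | Mean percent change | Interval wholly above 0 | Same, log ratio |
|---|---|---|---|
| 0.1 | +1.0% | 4.3% | 2.4 to 2.5% |
| 0.2 | +4.1% | 6.7% | 2.4 to 2.5% |
| 0.3 | +9.4% | 10.2% | 2.4 to 2.5% |
| 0.5 | +28.4% | 18.5% | 2.4 to 2.5% |

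With a true 25% fall and s = 0.3, the treated arm averages 0.75 × exp(0.09) - 1 = -17.9%.

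**Step 3: between-arm comparison.** For s = 0.1 / 0.2 / 0.3 / 0.5, type I error is 4.9 / 4.9 / 4.9 / 4.6%. With a true 25% fall the contrast averages -25.3 / -26.0 / -27.4 / -32.0 points, and its interval covers -25 in 95.1 / 94.9 / 94.8 / 95.2% of trials.

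**The case against.** The strongest reply is that the planned inference is sound. The objective is a between-arm comparison, the only analysis given an alpha is the ANCOVA, and Step 3 shows that comparison to be essentially unaffected by skewness. A reader might infer from Step 2 that the treatment comparison is biased towards a rise. It is not: when both arms vary equally the lean cancels under no effect.

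A reader might also infer that the per-arm intervals are miscalculated. The protocol's own summary is the arithmetic mean percent change, whose true value in this model is +1 to +28%, not zero. The planned interval covers that value in 94.9 / 94.5 / 93.9 / 91.5% of arms at s = 0.1 / 0.2 / 0.3 / 0.5. The 2.5% benchmark applies only if the geometric mean is the target.

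Further, quartiles are planned in the same tables. The median averages only +0.1 to +1.6% in the no-change case, so it exposes the skew, though it comes without an interval. Observed values are analysed too, and 8.2.2 gives absolute change for four serum lipids, so percent change is not the only measure of change for those. No variability is documented for any variable.

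All of this stands, and it limits the second issue to a supplementary presentation. None of it answers the first: the missing Week 0 covariate costs precision in the between-arm analysis itself.

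**Conclusion.** The ANCOVA omits an available pre-allocation covariate and loses some precision. The loss ranges from negligible to about 11 points of power at s = 0.3, and it is largest when between-subject spread is small relative to within-subject noise. This applies to all the ANCOVA variables, including LDL particle size.

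The lean in per-arm percent change is real only for concentration, particle-number and ratio variables, in full arms, and against a geometric target. It is small at s of 0.2 or less and material from about 0.3; which variables are that noisy is an assumption. It should not be carried over to LDL particle size, where *s* is presumably very small, or to the small triglyceride and age strata: with 5 to 8 patients the interval lies above zero in 1.5 to 2.8% of cases, so the excess disappears.

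The two remedies do different work. The log scale removes the lean; the Week 0 covariate does not, but it supplies most of the power gain when between-subject spread is small. This is an improvement to consider in an exploratory study, not a flaw that invalidates the planned comparison.

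**What to change.** 1. In SAP 7.1(5), 7.2 and 10.1, add the Week 0 value of the analysed variable as a continuous covariate beside the two stratification factors, for all variables including LDL particle size. Use log Week 0 where the log scale is used. No patient is lost, because percent change already requires the Week 0 value.

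2. Keep the percent-change tables and the percent-change ANCOVA. For concentration, particle-number and ratio variables (including TG/cholesterol in sdLDL and EPA/AA) in 7.1, 7.2 and 7.3, add as supplementary results the per-arm geometric mean percent change and the between-arm ratio of geometric means, each with a 95% interval. In 7.1 and 7.2, add a supplementary ANCOVA on ln(Week 8 / Week 0) with log Week 0.

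3. For the log analysis, do not use the value 0 that SAP 5 assigns to below-limit total cholesterol, TG and HDL-C, since its logarithm is undefined. Use the lower limit of quantification, as SAP 5 does for the other efficacy data.

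The cost is SAP wording and programming, one extra set of summaries and one degree of freedom. No new data are needed, and Protocol 13.1.3 is not contradicted, because its tables stay and the ANCOVA appears only in the SAP.
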